6.2. Adjustments for Covariates

Stratification factors of this study include country, HbA1c stratum ($\leq 8.0\%$, $> 8.0\%$), type of basal insulin during the lead-in period (glargine or degludec), and number of prandial doses at study entry (< 3 , ≥ 3). Stratification factors will be entered into the IWRS for randomization and also collected in the database by electronic case report form (eCRF) or central laboratory. The analysis models will use the stratification factors as collected in the database.

For the primary analysis of HbA1c, the stratification factor of HbA1c stratum will not be included. Instead, the continuous value of baseline (Visit 8) HbA1c will be included in the analysis models.

For analyses of the incidence and rate of hypoglycemia, the baseline hypoglycemia event rate with the same category of the dependent variable will be included as a covariate in the analysis models.

Other efficacy analyses will include the stratification factors as noted in Sections 6.11 and 6.12.

6.3. Handling of Dropouts or Missing Data

The analyses for the primary and multiplicity adjusted objectives will be performed for the intention-to-treat (ITT) estimand including all data collected through Week 26 regardless of IP use and the efficacy estimand including data collected prior to permanent discontinuation of IP through Week 26.

CCI

CCI

6.4. Multicenter Studies

Countries in similar geographic regions with fewer than 10 patients, based on the Randomized Population, will be pooled to achieve a pooled country of at least 10 patients. All analyses using country in the model will use a pooled country, unless otherwise specified. According to the blinded data, only Italy could not meet the requirement of 10 randomized patients. Therefore, Italy and Spain will be pooled as one pooled country for analysis.

CCI

6.5. Multiple Comparisons/Multiplicity

A graphical approach for multiple comparisons will be used to strongly control the overall Type I error (2-sided alpha level of 0.05) for testing the treatment effect for the primary and the multiplicity adjusted objectives given in Section 4. See Section 6.11.2 for the details of graphical testing scheme.

No multiplicity test adjustment will be made for other objectives.

6.6. Patient Disposition

Patient disposition will be displayed in a flowchart showing the number of patients entered, enrolled, randomized, and discontinued across all study periods.

Frequency counts and percentages of all randomized patients completing and discontinuing from the study will be presented for each treatment group. Reasons for discontinuation from the study and study treatment during the 26-week treatment period will be compared between treatment groups using Fisher's exact test. Reasons for discontinuation from the study at Visit 801 will be summarized by the randomized treatment groups.

Frequency counts and percentages of all patients entered, enrolled, and discontinued from the study during the lead-in period will be summarized. Reasons for discontinuation during screening will be summarized for all entered patients. Reasons for discontinuation from the study during the lead-in period will be summarized for all enrolled patients.

Time to all-cause discontinuation (discontinuation for any reason) from the study and from study treatment will be compared between treatment groups for the 26-week Treatment Period. The Kaplan-Meier product limit method will be used to create survival curves and the log-rank test will be used for the treatment comparisons. Time to all-cause discontinuation is defined as the total number of days between the randomization date (Visit 8 date) and date of discontinuation plus 1. Patients who complete the treatment period will be treated as censored using the total number of days between the randomization date and the Visit 18 date plus 1. If sufficient numbers of patients discontinue the study because of AE, similar analysis will be performed for time to discontinuation due to AE.

A listing of the primary reason for treatment discontinuation (if applicable) and study discontinuation will be generated for the Enrolled Population.

Patient allocation by investigator, grouped by country, will be summarized indicating the number of patients who enter the study, the number of patients who participate in the lead-in period, the number of patients who are randomized to study treatment, and the number of patients who discontinue the study during the 26-Week treatment period.

A listing of the randomization treatment assignment will be generated for all randomized patients.

6.7. Patient Characteristics

A summary table will be generated for patient characteristics at study entry using all randomized patients. The following variables will be included but not limited to: age, age groups (<40 and ≥40 years, and <65, ≥65 to <75, ≥75 to <85, ≥85 years), sex, country, ethnicity, race, height, weight, body mass index (BMI), BMI groups (<25, ≥25 to <30, ≥30 to <35, and ≥35 kg/m²). For continuous variables, the following statistics will be provided: mean, SD, minimum, maximum, and median, and treatment groups will be compared using an analysis of variance (ANOVA) model with a term of treatment. For categorical variables, summary statistics will include sample size, frequency and percentage, and treatment groups will be compared using Fisher's exact test or Pearson's chi-square test. A listing of patient characteristics at study entry will be provided.

A similar summary of diabetes characteristics will also be generated. The following variables will be included but not limited to: duration of diabetes, the type of prandial insulin at study entry, the type of basal insulin therapy at study entry (including whether given once daily [QD] or twice-daily [BID]) and randomization, the type of pre-mix insulin at study entry, number of prandial injections at study entry (<3, ≥3), oral antihyperglycemic medication (OAM) use at study entry and randomization, prandial insulin dosing plan, HbA1c at study entry and baseline, HbA1c stratum (based on measurement at baseline), and fasting serum glucose at Visit 2 and baseline (based on mixed-meal tolerance test [MMTT]).

A listing of patients whose stratification factor value entered into the IWRS (for treatment group assignment) is different from the clinical database will also be provided.

For all randomized patients, the number and percentage of patients with historical conditions will be summarized by treatment group using Medical Dictionary for Regulatory Activities (MedDRA) PT (without regard to SOC), and the number and percentage of patients with preexisting conditions will also be summarized by treatment group using MedDRA PT (without regard to SOC). Historical conditions are conditions that end prior to inform consent and preexisting conditions are conditions that are still ongoing at inform consent. Events will be ordered by decreasing frequency. No statistical comparisons between treatment groups will be performed.

6.8. Treatment Compliance

No analysis for treatment compliance is planned for this study.

6.9. Important Protocol Deviations

Important protocol deviations (IPD) that potentially compromise the data integrity and patients' safety will be summarized by treatment group for all randomized patients. Patients with more than one IPD from the same category, subcategory, and study-specific term (description) will only be counted once per patient.

[Table 6.3](#) lists the categories/subcategories of important protocol deviations, source of identification, and the method to identify each deviation.

Table 6.3. Description of Important Protocol Deviations

Category	Sub-categories	Description	CCI	Methods of Identification
Informed Consent	Informed Consent Not Obtained		CCI	Applicable to main protocol. Compare all assessment dates to ICD date (except those assessments that may occur before ICD, e.g. disease assessments).
Informed Consent	Improper Consent		CCI	Applicable to main protocol. Failure to re-consent after an ICD amendment at first possible visit. Unauthorized personnel administered ICD. Patient signed incorrect version of ICD. ICD was not dated. ICD was lost.
Informed Consent	Revoke Consent		CCI	Applicable to main protocol. Patient revoked ICD.
Eligibility	Inclusion/Exclusion	Type of patient and disease characteristics	CCI	CRF Medical History, Diabetes Duration panel data to indicate diagnosis date of T2D per protocol <1 year prior to screening date. CCI
Eligibility	Inclusion/Exclusion	Age not in compliance with entry criteria	CCI	CRF data to indicate the age <18 yrs at Visit 1. CCI
Eligibility	Inclusion/Exclusion	HbA1c not in compliance with the entry criteria	Programmable (clinical database)	Central Laboratory data to indicate that entry HbA1c not compliant with entry criteria #5.

Description of Important Protocol Deviations

Category	Sub-categories	Description	Source	Methods of Identification
Eligibility	Inclusion/Exclusion	Hematological conditions	Mixed (monitoring and clinical database)	CRF Pre-existing Conditions panel data using MedDRA terms that are considered as relevant hematological conditions by the CRP/CRS to indicate not compliant with entry criteria #29. CCI [REDACTED]
Eligibility	Inclusion/Exclusion	Previous noninsulin antihyperglycemic medications	Mixed (monitoring and clinical database)	CRF Prior Diabetes Therapies / Concomitant Therapy panel data to indicate not compliant with entry criteria #31, #4. CCI [REDACTED]
Eligibility	Inclusion/Exclusion	Previous insulin therapy	Mixed (monitoring and clinical database)	CRF Prior Diabetes Therapies / Concomitant Therapy panel data to indicate not compliant with entry criteria #3, #32, #33. CCI [REDACTED]
Investigational Product	Treatment Assignment/ Randomization Error		Mixed (monitoring and clinical database)	IWRS data entry errors that impact patient stratification, for example, lab data indicated different strata from IWRS stratification report. Dispensing error: Patient is assigned to a treatment, but site gave a different treatment to the patient.
Investigational Product	Unblinding		Non Programmable (monitoring)	Any inadvertent unblinding affecting patients, investigator or sponsor.
Investigational Product	Patient Took Medication Not Fit for Use		Non Programmable (monitoring)	Study Drug not fit for use administered to patient.
Investigational Product	Other	Use of expired CT material	Non Programmable (monitoring)	CCI [REDACTED]

Description of Important Protocol Deviations

Category	Sub-categories	Description	Source	Methods of Identification
Study Procedures	Violation of Discontinuation Criteria		Mixed (monitoring and clinical database)	Patients not discontinued from treatment and/or study despite having met protocol specified discontinuation criteria. CCI [REDACTED] Protocol Section 8.
Study Procedures	Excluded Conmeds		Mixed (monitoring and clinical database)	CRF Prior Diabetes Therapies / Concomitant Therapy panel data to indicate not compliant with entry criteria #34 and study-specific restriction on concomitant therapies Table ITRN.8 in the study protocol. CCI [REDACTED]
Study Procedures	Lab/Imaging Criteria	Missing HbA1c at baseline/at the primary endpoint	Mixed (monitoring and clinical database)	Central laboratory data to indicate that a). HbA1c is not collected at both Visit 7 and Visit 8 or b). HbA1c is not collected at the primary endpoint (only applicable to patients who completed the primary endpoint without early discontinuation from the study).
Study Procedures	Visit Schedule Criteria		Programmable (clinical database)	CRF Subject Visit panel data to indicate that 2 consecutive office visits are completely missing.
Study Procedures	Other	Electronic Clinical Outcomes Assessment (eCOA)	Programmable (clinical database)	Comparison of patient data from CRF and eCOA to identify randomized patients who have no ed diary data entered.
Administrative/Oversight	Suspected Misconduct		Non Programmable (monitoring)	Site staff sharing account details for systems (e.g. IWRS, EDC or ePresentOnline). Suspected falsification of data.

Description of Important Protocol Deviations

Category	Sub-categories	Description	Source	Methods of Identification
Safety	Safety Mailings		Non Programmable (monitoring)	Lack of, significant delay in safety mailing review (significant delay defined as a delay of 90 days).
Safety	SAEs		Non Programmable (monitoring)	Failure to report an SAE within 24 hours of the investigator being made aware of the SAE. Failure to respond to SAE queries.
Safety	Other	Failure to report product complaint within 24 hours	Non Programmable (monitoring)	CCI [REDACTED]

Abbreviations: # = number of inclusion/exclusion criteria in protocols; CCI [REDACTED]; CRF = clinical (case) report form; CRP = clinical research physician; CRS = clinical research scientist; CT = clinical trial; eCOA = electronic clinical outcomes assessment HbA1c = hemoglobin A1c; ICD = informed consent document; EDC = Electronic Data Capture; IWRS = interactive Web Response System; MedDRA = Medical Dictionary for Regulatory Activities; SAE = serious adverse event; CCI [REDACTED] T2D = type 2 diabetes; yrs = years.

CCI [REDACTED]

- [REDACTED]
- [REDACTED]
- [REDACTED]

[REDACTED]

[REDACTED]

6.10. Concomitant and Prior Therapy

Concomitant medication will be summarized and compared between treatment groups using Fisher’s exact test for the Randomized Population during the treatment period. The percentages of patients receiving each concomitant medication will be summarized by treatment using PT nested within Anatomical Therapeutic Chemical (ATC) Level 3 code. Medications will be ordered by decreasing frequency within ATC level. Concomitant medication used during the lead-in period will also be summarized for the Enrolled Population.

A summary of previous diabetes therapies that were discontinued prior to informed consent will be generated for the Enrolled Population.

Total daily basal and total daily prandial insulin doses for the day prior to Visit 2 will be entered into the eCRF. The daily basal doses and individual prandial insulin doses (that is, morning meal, midday meal, evening meal, bedtime/snack/other) will be entered into the electronic clinical outcomes assessment (eCOA) device after Visit 2. At a given visit, total daily basal insulin dose to be used for analysis will be calculated as the mean of the total daily basal insulin doses on the 7 days prior to the visit date (or the days between the previous visit date and the current visit date if the number of days between the 2 visit dates is <7). Similarly, the dose for each meal will be calculated as the mean of the doses on the 7 days prior to the visit date (or the days between the previous visit date and the current visit date, whichever smaller). Total daily prandial insulin dose to be used for analysis will be calculated as the sum of the individual meal insulin doses. If either total daily basal insulin dose or total daily prandial insulin dose is missing, total daily insulin dose and prandial/total insulin dose ratio will be set as missing for analysis.

Total daily basal insulin dose, total daily prandial insulin dose, total insulin dose, and the ratio of prandial insulin dose to total insulin dose during the lead-in period will be summarized by visit for the Randomized Population. The actual and change from Visit 2 values will be compared between treatment groups using an MMRM model including the corresponding dose at Visit 2, treatment, strata (pooled country, type of basal insulin, the number of prandial doses at study entry and HbA1c stratum), visit, treatment-by-visit interaction in the model as fixed factors and patient as a random factor. Doses will be summarized in U and U/kg. Basal insulin dose will be summarized independently for glargine and degludec as well as combined.

Up to 3 OAMs (metformin, dipeptidyl peptidase-4 inhibitor [DPP-4] inhibitor, sodium-glucose co-transporter 2 [SGLT2] inhibitor, sulfonylurea, meglitinide and alpha-glucoside inhibitor) are allowed prior to the study, and up to 2 OAMs (metformin and SGLT2 inhibitor) are allowed during the lead-in and treatment periods. The proportion of patients who were treated with OAMs (by class of OAM) at each visit will be summarized and compared between treatment groups using Fisher's exact test. The number of OAMs per patient will also be summarized by treatment and by period: lead-in period (Visit 2 to Visit 8) and treatment period (Visit 8 to Visit 18).

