9.1.4.1. Electronic Clinical Outcomes Assessment

The eCOA diary will collect all glucose data directly from the BG meters, thereby increasing the validity of measures reported by the patient and minimizing transcription errors in recording the measures. The use of e-diaries should also allow more complete and accurate capturing of hypoglycemia events, as well as more frequent and timely interactions between investigator and patients as the intensity of their individual diabetes management increases. The system will be used to collect prandial insulin doses (date, time, and actual dose taken) and the basal insulin dose, on the 3 days prior to study visits, on the days of 10-point SMBG profiles, and at other times as clinically indicated. Hypoglycemic events will be captured throughout the clinical study in eCOA along with date and time of the BG level if measured and hypoglycemia treatment and outcome data. Additionally, the eCOA system will incorporate study-specific reminders for patients to perform the 10-point SMBG profiles.

Physicians and designated clinical staff will have access to the eCOA portal (secure web-based site) with the ongoing near real-time updating of BG readings, insulin doses administered, and hypoglycemic events. Manual inspection of data will support at least weekly patient monitoring as an enhancement to standard of care for patient safety, as well as the potential for reaching an optimum efficacy outcome. Investigative staff will assess clinical data via the eCOA portal and recommend adjustments in basal and prandial insulin (also refer to Section 7.2.1).

An instruction manual will be provided to patients and investigative sites. Additional instruction and training will be provided to the investigative sites regarding data collection, review, retention and archival processes. In the event of eCOA malfunction or loss, the patient will be instructed to immediately contact the investigative site for instructions regarding replacement of the equipment.

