9.1.4.3. Ten-Point Self-Monitoring Blood Glucose

Patients in both study groups should be instructed to perform 10-point SMBG profiles prior to 5 visits during the study (Visits 8, 11, 13, 15, and 18). Three 10-point profiles should be done during the 2 weeks prior to each visit. Each 10-point profile during this 2-week time interval should be completed over a 1-day period, preferably on 3 nonconsecutive days (weekdays and weekends), as per the Schedule of Activities (Section 2). The 10-point profile consists of 10 SMBG measurements on the same day at premeal, 1-hour, and 2-hours after the start of the morning, midday, and evening meals, and at bedtime. The 10-point SMBG profile is inclusive of the daily 4-point SMBG readings. Patients should be encouraged to eat a morning, midday, and evening meal on the days that the 10-point SMBG is monitored. Premeal measurements should be taken before the patient begins eating the meal. Patients may eat a snack and cover with bolus insulin if that is their usual practice. Missing values in 10-point SMBG profiles will not be considered protocol deviations unless, in the opinion of the investigator, they are excessive and reflect noncompliance with the protocol.

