6.11.5. Other Secondary Efficacy Analyses

The analyses described in Section 6.11.5 to Section 6.11.7 will include data collected from all randomized patients prior to permanent discontinuation of IP. The longitudinal observations of actual and change from baseline in HbA1c up to Week 26 will be analyzed using the same MMRM model as for the analysis of the primary outcome. For the following secondary efficacy endpoints, an MMRM model similar to that for the primary outcome with an additional term of HbA1c stratum ($\leq 8\%$, $> 8\%$) will be used:

- actual and change from baseline 1,5-AG values
- actual and change from baseline 10-point SMBG values (fasting, 1 hour post morning meal, 2 hours post morning meal, pre midday meal, 1 hour post midday meal, 2 hours post midday meal, pre evening meal, 1 hour post evening meal, 2 hours post evening meal, and bedtime)
- actual and change from baseline in total, basal, and prandial insulin doses and prandial/total insulin dose ratios

Three 10-point SMBG profiles are expected to be collected during the 2 weeks prior to specified visits. Valid SMBG profiles will be used for analysis, defined as having non-missing values at ≥ 6 time points among the 10 pre-specified time points and being collected during 2 weeks prior to a given visit. For each time point, the average of the corresponding SMBG values from the valid SMBG profiles will be used for analysis. The excursion of SMBG for each meal category (that is, morning meal, midday meal, and evening meal) calculated using the average values at the corresponding time points will be used for analysis.

The following endpoints, collected from the MMTT, will be analyzed using the ANCOVA model with strata (pooled country, type of basal insulin, number of prandial doses at study entry, and HbA1c stratum) and treatment as fixed effects and baseline as a covariate:

- actual and change from baseline in fasting glucose (average of measurements at time -15 and 0), and PPG at 15, 30, 60, 120, 180, and 240 minutes after the meal
- PPG excursions at time 15, 30, 180, and 240 minutes after the meal (PPG minus fasting glucose)

Sensitivity analysis for PPG excursions may be performed to exclude patients whose PPG excursion could be affected by factors including MMTT consumption amount (for example, partial MMTT was consumed) and correction bolus insulin usage.

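### Does SAP 6.10 count an occasional bedtime or snack bolus as if it were taken every day?

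*SAP*

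**What the plan says.** The dose derivation is in SAP 6.10. After Visit 2, daily basal doses and "individual prandial insulin doses (that is, morning meal, midday meal, evening meal, bedtime/snack/other") are entered in the electronic diary. The basal value at a visit is the mean of the daily basal totals over the 7 days before it, or over the interval since the previous visit if that is shorter. The next sentence is introduced as parallel to the basal rule: "the dose for each meal will be calculated as the mean of the doses on the 7 days prior to the visit date", with the same shortening. Then: "Total daily prandial insulin dose to be used for analysis will be calculated as the sum of the individual meal insulin doses". The only missing-data rule in this derivation acts on the basal and prandial totals, not on a single category or day.

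For Visit 2 the source differs: "Total daily basal and total daily prandial insulin doses for the day prior to Visit 2 will be entered into the eCRF".

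Protocol 9.1.4.1 has the diary "collect prandial insulin doses (date, time, and actual dose taken) and the basal insulin dose". It requires this on the 3 days before visits, on 10-point profile days, and when clinically indicated. Protocol 7.2.1.4 expects three prandial doses with three main meals a day. On 10-point profile days, Protocol 9.1.4.3 adds: "Patients may eat a snack and cover with bolus insulin if that is their usual practice".

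The derived doses serve secondary objective 10, analysed under SAP 6.11.5 as "actual and change from baseline in total, basal, and prandial insulin doses and prandial/total insulin dose ratios". They also enter the lead-in comparison in SAP 6.10 ("The actual and change from Visit 2 values will be compared between treatment groups using an MMRM model") and the antibody-status subgroup analysis in SAP 6.12.7.1.

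**The concern.** Averaging by category and then adding gives the same answer as adding within each day and then averaging only if every category is filled once on every recorded day. That is a fair expectation for the three main meals but not for bedtime/snack/other, which many patients will leave empty on most days. The SAP gives no zero for such days, no denominator, no rule for two snack boluses on one day, and no rule for a category with no entries.

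If a mean of doses is taken to be the mean size of the boluses entered, one bolus in the window counts as a daily one. Prandial dose, total dose and the prandial/total ratio would then be misstated for patients with irregular boluses. Basal dose would not. A change in how often a patient takes a bolus would also be misread as a different change in dose, or as none.

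**Working it through.** The plan gives no figure for this derivation, so there is none to reproduce. The check compares the two readings.

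**Inputs.** From the documents: four dose categories and the order of averaging (SAP 6.10); recorded days k from 3 (required by Protocol 9.1.4.1) to 7 (the SAP window). Assumed, because the documents give no doses or bolus frequencies: main meals M = 45 U/day, basal 50 U/day, bolus size s = 6 U (range 4 to 10 U), n boluses over the k recorded days.

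**Formulas.**
- Entered doses only: prandial = M + s, whenever n is at least 1.
- Per recorded day: prandial = M + s × n/k.
- Difference: s × (1 − n/k). It is zero when n = k.

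**Level at one visit (M = 45).**

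| s | n | k | Entered doses only | Per recorded day | Difference |
|---|---|---|---|---|---|
| 6 | 1 | 3 | 51 | 47 | +4.0 (4/47 = 8.5%) |
| 6 | 2 | 3 | 51 | 49 | +2.0 (4.1%) |
| 6 | 3 | 3 | 51 | 51 | 0 |
| 6 | 6 | 3 | 51 | 57 | −6.0 (−10.5%) |
| 4 | 1 | 3 | 49 | 46.33 | +2.67 (5.8%) |
| 10 | 1 | 3 | 55 | 48.33 | +6.67 (13.8%) |
| 6 | 1 | 7 | 51 | 45.86 | +5.14 (11.2%) |
| 10 | 1 | 7 | 55 | 46.43 | +8.57 (18.5%) |

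In the first row the total dose is 101 against 97 U (4/97 = 4.1%), and the ratio is 51/101 = 0.505 against 47/97 = 0.485.

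**Change from Visit 8 (s = 6, k = 3).**
- Same bolus frequency at both visits: the offset cancels and the error is 0.
- 1 of 3 days to 3 of 3 days: 51 − 51 = 0, against 51 − 47 = +4.
- No bolus to 1 of 3 days: 51 − 45 = +6, against 47 − 45 = +2. The +6 needs a mixed convention: a wholly empty category counts as 0 U, but empty days in a partly filled category are dropped. The SAP states neither half.

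**Lead-in.** Visit 2 is a one-day total, expected to average 47 U for a patient with 6 U on one day in three. Later visits would read 51 U, an apparent rise of about 4 U with no change in dosing. Per recorded day the rise is 0 on average.

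**Between arms.** Assume 5 to 10 percentage points more patients in one arm have the first-row pattern. The difference in mean dose is 4.0 × 0.05 = 0.2 to 4.0 × 0.10 = 0.4 U/day, about 0.2% to 0.4% of a 97 U total. The ratio moves by 0.0204 × 0.05 = 0.001 to 0.0204 × 0.10 = 0.002. At the largest offset in the table, 8.57 × 0.10 = 0.86 U/day, or about 0.9% of a 96.4 U total.

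**Which reading the text supports.** The basal rule is a mean of daily totals, and the prandial sentence is tied to it as a like rule. Each category is then a mean per day, over the days recorded. The empty category points the same way. A patient who never takes a snack bolus has no doses to average, so a total can be formed only by counting the blank as 0 U. Once a blank means none taken in that case, the natural reading of a blank on any recorded day is the same.

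**The case for a change.** The strongest case for a change is that the text leaves several defensible programs open, and they give different values of a named endpoint. The basal rule adds within the day first and the prandial rule does not. Dividing by a fixed 7 is not an obvious default when only 3 days of entry are required. An unthinking program could average non-blank entries and then add non-blank averages, which is exactly the mixed convention above. The SAP is more exact elsewhere, for instance on valid 10-point profiles and on merging hypoglycemia events. A clarifying sentence would cost little.

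The omission is real and the arithmetic stands. What does not follow is that the plan yields a wrong result. The error exists only under one reading, and not the most natural one. Whether the diary stores an explicit zero or a single daily bedtime/snack/other field is not in either document, and that alone could settle the matter. The lead-in mismatch predates randomization, when all patients take open-label lispro, so no arm difference there can reflect treatment.

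Extra wording is not free of traps either. A rule applied only from Visit 8 would miss the earlier lead-in visits, since Table 6.2 uses Visits 3 to 8. A rule for snack boluses alone would leave the same question for a skipped main meal. And a bolus taken but not entered would become 0 U.

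**Conclusion.** No change to the plan is needed. SAP 6.10 leaves a derivation detail open; it does not prescribe a wrong calculation. Averaging per recorded day, with no entry counted as none taken and same-day boluses added together, is the ordinary way to compute a daily dose and gives no error.

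Under the other reading, individual values could be off by several units: +4 U (8.5% of prandial dose) in the central example, and +2.7 to +8.6 U for a single 4 to 10 U bolus over 3 to 7 recorded days. These sizes rest on assumed doses and bolus frequencies. A stable offset cancels in the change from Visit 8, and the same rule applies to both blinded arms. The arm difference would be 0.2 to 0.4 U/day under an assumed 5 to 10 point imbalance, and 0.86 U/day at the extreme shown.

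The effect is confined to objective 10 (which SAP 6.5 leaves without multiplicity adjustment), the lead-in dose summaries and the dose-by-antibody subgroup analysis. HbA1c noninferiority, HbA1c superiority and the postprandial excursion tests do not use the derived dose.
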